11.2.3. Efficacy Analysis Set

The efficacy analysis set will include all subjects who received at least one dose of the study drug and who underwent efficacy evaluation after administration at least once.

11.2.4. Pharmacokinetic Analysis Set

The pharmacokinetic analysis set will include subjects who received at least one dose of the study drug, whose specimens for pharmacokinetics have been collected at least once after the start of treatment, and who have available data of the measurement.

11.2.5. Biomarker Analysis Set

The biomarker analysis set will include subjects who received at least one dose of the study drug, whose specimens for biomarker research have been collected, and who have available data of the measurement.

11.3. Data Handling

The sponsor will decide the handling of individual data in consultation with the medical expert as needed, and lock data.

11.4. Statistical Analysis Items and Methods

11.4.1. Baseline Subject Characteristics

For baseline subject characteristics (demographic variables and baseline values), distributions and summary statistics will be calculated. Frequency tables will be prepared for categorical data and summary statistics will be calculated for quantitative data. Analyses will be performed in the safety analysis set, MTD analysis set, efficacy analysis set, pharmacokinetic analysis set, and biomarker analysis set.

11.4.2. Safety Analysis

Safety will be analyzed in the safety analysis set, unless otherwise noted. AEs that occur or worsen relative to the pre-treatment state after the start of study treatment (TEAEs) will be tabulated. AE terms will be converted using the Medical Dictionary for Regulatory Activities (MedDRA) terminology developed by the ICH. Individual AEs will be grouped by organ system using the system organ classes (SOC) of MedDRA, and be summarized in the preferred term (PT) level.

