- Prophylactic treatment for the following symptom is prohibited during the DLT evaluation period. However, treatment given as supportive care for the following symptom is allowed.
Neutropenia: Granulocyte colony stimulating factor (G-CSF) products etc.

Study procedures:	Refer to Appendix 1 .
Study Endpoints:	
Safety endpoints:
 
Adverse events (AE), ECOG PS, laboratory data, body weight, vital signs, and 12-lead ECG

	
Efficacy endpoints:
 
Complete remission (CR), CR with incomplete hematological recovery (CRi), CR with partial hematological recovery (CRh), partial remission (PR), morphologic leukemia-free state (MLFS), stable disease (SD), progressive disease (PD), composite CR (CRc) rate (CR + CRi + CRh), response rate (CRc + PR), and duration of CRc

Pharmacokinetic endpoints:

Plasma DS-3032a concentration and pharmacokinetic parameters (Subtrial A)

C1D1 (Cycle 1 Day 1): Cmax, Tmax, AUClast, AUC8h, AUC24h, AUCinf*, Kel*, t1/2*, CL/F*, Vz/F*

C1D14 (Cycle 1 Day 14)**: Cmax, Ctrough, Cavg, Tmax, AUC8h, AUC24h, Kel*, t1/2*, CLss/F***, Vz/F****, AR

*: To be calculated only if possible.

**: To be read as C1D7 (Cycle 1 Day 7) in Subtrial B, C1D3 (Cycle 1 Day 3) in Subtrial C, and C1D15 (Day 15) in Subtrial D.

***: Not to be calculated because steady state will not be reached in Subtrial C.

Pharmacodynamic endpoints:

Tumor protein p53 gene (*TP53*) mutation and serum macrophage inhibitory cytokine-1 (MIC-1) level

Primary statistical analyses:

Safety analyses:

The DLT rate will be estimated for each dose using mCRM based on DLT evaluation data of all evaluable subjects, and the MTD will then be determined. AEs that occur or worsen after the start of study treatment will be summarized in frequency tables by event, causality with the study drug, and grade according to the CTCAE. For laboratory data, vital signs, body weight, and 12-lead ECGs, a frequency table or shift table will be prepared for categorical data and summary statistics will be calculated for quantitative data. Also, frequency table(s) with detailed descriptions of DLTs (if any) will be prepared.

Efficacy analyses:

Frequency tables will be prepared for best response. The CRc rate, response rate, and transplantation rate will be calculated. Summary statistics will be calculated for the duration of CRc.

Pharmacokinetic analyses:

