3.2. Explorative Dose Finding in Each Subtrial

After confirming the DLT rate in Cycle 1 in each cohort in accordance with “Section 5.3.1 Definition of Dose-limiting Toxicities,” the dose for the next and subsequent cohorts will be determined, in consideration of the following i) and ii). As a rule, each cohort consists of 3 to 6 subjects, and if “Section 5.4 Enrollment of Additional Subjects” is applicable, enrollment of additional subjects will be considered.

- i) Recommended dose, guided by mCRM using a Bayesian logistic regression model (BLRM) incorporating the EWOC principle
- ii) Clinical evaluation of the toxicological profile and information on pharmacokinetics/pharmacodynamics (PK/PDy)

Rationale:

The study design was selected in reference to the “Guidelines for Clinical Evaluation of Anticancer Drugs.¹⁷” The Bayesian statistical analysis methods are specified in “Section 11.7 Details of Modified Continual Reassessment Method.”

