9.3. Adverse Event Information to be Reported

If an AE occurs during the study, the items shown in “[Table 9.3.1 Adverse Event Information to be Reported](#)” will be investigated and recorded in the case report form. If a medical interview is used to investigate symptoms, questions that specify symptoms should not be used. If a subject has two or more signs (including symptoms and abnormal changes in laboratory data) that are correlated with each other and can be considered part of one diagnosis, they will be regarded as one single event, and the diagnosis will be recorded as an AE in the case report form. Only the highest grade observed in the course of each AE should be recorded as the severity in the case report form.

AEs will be graded according to the “CTCAE Version 5.0.” AEs that are not listed in the CTCAE Version 5.0 will be graded according to the definitions provided in “[Table 9.3.1 Adverse Event Information to be Reported](#).”

Table 9.3.1: Adverse Event Information to be Reported

Item	Details to be Assessed		
AE	Name of AE, date of onset		
Action taken for AE	Whether or not action was taken (including the modification of administration of the study drug), and if taken, details of the action.		
Outcome	Outcome category, date of outcome assessment, date of resolution		
	Outcome category	
Recovered/ Resolved
 
Recovering/ Resolving
 
Not recovered/ Not resolved
 
Recovered/ Resolved with sequelae/ residual effect(s) present
 
Fatal
 
Unknown
	
The AE has resolved, and the subject has recovered to the pre-event condition.
 
The AE has almost resolved, and the subject has nearly recovered to the pre-event condition.
 
The AE has not resolved, and the condition of the subject is similar to that at onset (unchanged).
 
The AE has resolved, but the subject has sequelae.
 
Tumor progression will not be handled as an AE. However, tumor progression leading to a fatal outcome during the AE collection period should be handled as a SAE (with the name and outcome of the event recorded as “disease progression” and “fatal,” respectively).
 
Outcome is unknown because of lack of information.

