11. STATISTICAL ANALYSIS

An outline of the statistical and pharmacokinetic analyses is provided below. Statistical methods will be specified in more details in the separately prepared Statistical Analysis Plan.

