11.1. General Statistical Considerations

Patients treated with the same dose level and schedule will be pooled into a single treatment group. All statistical analyses will be performed by treatment group, unless otherwise noted. Subjects whose dose is reduced will be analyzed in the dose group before dose reduction.

Baseline values of each subject, unless otherwise specified, will be the last observed values that are available before the first dose of the study drug.

Unless otherwise noted, continuous variables will be summarized by the number of subjects analyzed, arithmetic mean, standard deviation, minimum, median, and maximum, whereas categorical variables will be summarized by frequency and proportion.

Analyses of changes from baseline (eg, absolute change, shift table) will be performed for subjects with the baseline value and at least one value available after treatment. Two-sided 95% confidence interval (CI) will be determined, unless otherwise noted.

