11.4.2.1. Adverse Events

For TEAEs and AEs assessed as “related” to the study drug, frequency tables will be prepared as classified below. The grade of AEs will be assessed according to the CTCAE Version 5.0. In the tabulation by grade, only the highest-grade event in each subject will be counted for tabulation.

- Subjects with TEAEs (by grade; including events classified as Grade ≥ 3)
- Subjects with serious TEAEs
- Subjects who have interrupted study treatment because of a TEAE
- Subjects withdrawn from study treatment because of a TEAE

For TEAEs and TEAEs assessed as “related” to the study drug, frequency tables will be prepared by event as classified below. The grade of AEs will be assessed according to the CTCAE Version 5.0. If a subject reports a single event two or more times, only the highest-grade event will be counted for tabulation.

- TEAEs
- TEAEs by grade (including events classified as Grade ≤ 2 and Grade ≥ 3)
- Serious TEAEs
- TEAEs leading to interruption of study treatment
- TEAEs leading to discontinuation of study treatment

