11.4.2.3. Laboratory Data

For hematology and blood chemistry tests, summary statistics of measured values and changes from baseline will be calculated at each scheduled time point. For urinalysis (qualitative data), shift tables of measured values at baseline and those at each time point will be prepared. For urinalysis (quantitative data), summary statistics will be calculated at each time point.

11.4.2.4. Height, Body Weight, and Vital Signs (Blood Pressure, Pulse Rate, and Body Temperature)

For blood pressure (systolic and diastolic), pulse rate, body temperature, and body weight, summary statistics of measured values and changes from baseline will be calculated at each time point.

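### Adverse events are tabulated by single preferred term only, so paired cytopenia terms can split one toxicity across two rows in very small dose groups

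*Combined protocol and SAP*

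**What the plan says.** Section 11.4.2 codes adverse events in MedDRA, groups them by system organ class, and states that they will "be summarized in the preferred term (PT) level". For the by-event tables, Section 11.4.2.1 adds: "If a subject reports a single event two or more times, only the highest-grade event will be counted for tabulation". The remaining tables in that section count subjects with any TEAE, any serious TEAE, or a TEAE that led to interruption or withdrawal. None of these is specific to a cytopenia. No grouped or combined term is mentioned.

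Section 11.1 sets the unit of reporting: "All statistical analyses will be performed by treatment group, unless otherwise noted". A treatment group is one dose level on one schedule, and Section 3.2 says "As a rule, each cohort consists of 3 to 6 subjects".

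Two laboratory outputs are planned alongside. The synopsis says that "a frequency table or shift table will be prepared for categorical data", a statement that covers laboratory data. Section 11.4.2.3 says: "For hematology and blood chemistry tests, summary statistics of measured values and changes from baseline will be calculated at each scheduled time point". Neither names a table of each subject's worst hematology grade.

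Section 11 presents itself as an outline: "Statistical methods will be specified in more details in the separately prepared Statistical Analysis Plan". That separate plan is not part of the text reviewed here.

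**The concern.** MedDRA offers two terms for the same laboratory finding: thrombocytopenia or platelet count decreased, neutropenia or neutrophil count decreased, leukopenia or white blood cell count decreased. Which one is recorded depends on how the investigator words the event. When both are used within a dose group, each gets its own row and its own worst grade. A reader can add the two rows only if no subject has both terms, and the planned tables do not show whether that is so.

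Safety and tolerability are the primary objective (Section 2), and Section 1.4 names blood and lymphatic disorders among the expected harms. With 3 to 6 subjects per cohort, one or two subjects moving between rows visibly changes the reported rate at a dose.

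The DLT tables cannot stand in for the missing row. Under the hematological criterion of Section 5.3.1, a cytopenia counts only if failed recovery delays Cycle 2 by more than two weeks, and febrile neutropenia is excluded. A severe cytopenia that recovers in time is not a DLT under that criterion, so the TEAE tables are a main place where it would be reported by dose.

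**Working it through.** **Inputs.** All counts come from the TEAE lists in Section 1.4 for the earlier studies U101 (n = 69) and J103 (n = 18).

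**Reproducing the printed figures.** 22/69 = 31.9%, 9/69 = 13.0%, 11/69 = 15.9%, 19/69 = 27.5%, 5/69 = 7.2%, 6/18 = 33.3% and 3/18 = 16.7% all match. The one exception is thrombocytopenia in U101, printed as 31.98%. Since 22/69 = 31.88%, this looks like a typing slip and changes nothing here.

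**Bounds.** If a and b subjects have the two terms, the number with either term is at least max(a, b), when overlap is complete, and at most min(n, a + b), when there is none.

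| Study, cytopenia | a, b | Lower bound | Upper bound | Gap (points) |
|---|---|---|---|---|
| U101 platelets | 22, 22 | 22/69 = 31.9% | 44/69 = 63.8% | 22/69 = 31.9 |
| U101 neutrophils | 9, 11 | 11/69 = 15.9% | 20/69 = 29.0% | 9/69 = 13.0 |
| U101 white cells | 5, 19 | 19/69 = 27.5% | 24/69 = 34.8% | 5/69 = 7.2 |
| J103 platelets | 6, 3 | 6/18 = 33.3% | 9/18 = 50.0% | 3/18 = 16.7 |

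The gap measures what the rows leave unknown. It is not a known error: at the lower bound the larger row is already correct, and at the upper bound the two rows simply add.

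**At this trial's cohort sizes (assumed counts).** Rows of 2/6 and 2/6 mean between 2 and 4 of 6 subjects, or 33.3% to 66.7%. Rows of 1/3 and 1/3 mean between 1 and 2 of 3, again 33.3% to 66.7%.

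**How often both rows would be used.** This needs assumptions. Let the true rate of platelet cytopenia be p, with each affected subject given one term, and let s be the share given the first term. Write p₁ = ps and p₂ = p(1 − s). The chance that both rows are non-empty in a group of n is

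1 − (1 − p₁)ⁿ − (1 − p₂)ⁿ + (1 − p)ⁿ.

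I took p from 0.319 to 0.638 (the U101 platelet bounds) and s of 1/3 (the J103 split) or 1/2 (the U101 split).

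| n | p = 0.319, s = 1/3 | p = 0.638, s = 1/2 |
|---|---|---|
| 3 | 11% | 42% |
| 6 | 35% | 80% |

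The other combinations of these values fall between the two columns.

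**Other planned output.** Section 9.3 says that, where a subject has two or more signs "that are correlated with each other and can be considered part of one diagnosis, they will be regarded as one single event". This reduces double recording within a subject. It does not exclude it over time, and it does not make different subjects or sites use the same term.

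**The case against.** The strongest reply is that the gap may not exist. Section 11 is an outline, grouping of terms is the kind of detail that normally sits in the separate SAP, and Section 11.4.2 does not say that preferred terms are the only level of summary. This stands as a condition: if that plan already groups the terms, nothing needs to change. As written, though, the protocol states a method, and that method splits the terms.

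Second, no decision depends on it. Section 5.3.1 and the interruption rules in Section 5.5.2 use neutrophil and platelet counts rather than coded terms. With 9 to 24 subjects in total (Section 11.6), an either-term count is a short tally from data already collected. This is correct and is why the point is modest.

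Third, the by-visit hematology summaries include minimum, median and maximum by treatment group (Section 11.1), so the depth of cytopenia at each visit is visible however events are coded. That is a real mitigation. However, a visit minimum does not follow a subject across visits, so it gives neither the number affected nor each subject's worst grade.

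Fourth, the evidence comes from other populations. U101 and J103 enrolled solid tumors and lymphomas. U102, in hematological malignancies and therefore closest to this trial, lists thrombocytopenia and neutropenia with no paired term, so the split may be smaller in AML and no bound can be given. In a group of 3, under the assumptions above, a split is the less likely outcome. J103 does show the platelet pair in Japanese practice.

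Fifth, U101 places the paired terms side by side and includes leukopenia at 7.2% in a list meant for events above 10%, which suggests that they were already viewed as pairs. Adjacent counts still do not give the number of subjects with either term.

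Finally, grouping three cytopenia pairs leaves other near-synonyms alone, such as fatigue (16 subjects) and asthenia (5) in U102. That is fair. The cytopenias are put first because they belong to an expected class of harm and both terms of each pair are documented with this drug.

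**Conclusion.** The concern holds. Under Sections 11.4.2 and 11.4.2.1 as written, if subjects in a dose group are coded to different terms of a cytopenia pair, no single row gives the number with that cytopenia or their worst grade. In the earlier data the rows leave between 7.2 and 31.9 percentage points undetermined, depending on the cell line and study.

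The effect is confined to preferred-term reporting of cytopenias. The DLT rate, the MTD and the any-TEAE worst-grade tables do not change. The conclusion depends on both terms being used within a group, which earlier data make plausible but do not establish for AML, and on the separate SAP not already grouping them. Confidence is medium. The change is worth making because safety is the primary objective and the cost is close to nothing.

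**What to change.** Keep the preferred-term tables. In Sections 11.4.2 and 11.4.2.1, add three pre-specified grouped terms, with each subject counted once at the highest grade across the group:

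- thrombocytopenia / platelet count decreased
- neutropenia / neutrophil count decreased
- leukopenia / white blood cell count decreased

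Show them in the all-TEAE, drug-related, Grade 3 or higher, and serious tables, by treatment group. Fixing the groups in advance avoids choosing them after the results are seen. If the separate SAP already does this, a cross-reference is enough.

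The cost is one sentence of analysis wording and a few table rows, using data already collected, with no extra visits or subjects. The downside for the sponsor is that reported cytopenia rates may look less favourable than the separate rows would.

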11.4.2.1. Adverse Events

For TEAEs and AEs assessed as “related” to the study drug, frequency tables will be prepared as classified below. The grade of AEs will be assessed according to the CTCAE Version 5.0. In the tabulation by grade, only the highest-grade event in each subject will be counted for tabulation.

- Subjects with TEAEs (by grade; including events classified as Grade ≥ 3)
- Subjects with serious TEAEs
- Subjects who have interrupted study treatment because of a TEAE
- Subjects withdrawn from study treatment because of a TEAE

For TEAEs and TEAEs assessed as “related” to the study drug, frequency tables will be prepared by event as classified below. The grade of AEs will be assessed according to the CTCAE Version 5.0. If a subject reports a single event two or more times, only the highest-grade event will be counted for tabulation.

- TEAEs
- TEAEs by grade (including events classified as Grade ≤ 2 and Grade ≥ 3)
- Serious TEAEs
- TEAEs leading to interruption of study treatment
- TEAEs leading to discontinuation of study treatment

11.4.2.2. Dose-limiting Toxicity

Frequency table(s) with detailed descriptions of DLTs (if any) will be prepared.

11.4.2.3. Laboratory Data

For hematology and blood chemistry tests, summary statistics of measured values and changes from baseline will be calculated at each scheduled time point. For urinalysis (qualitative data), shift tables of measured values at baseline and those at each time point will be prepared. For urinalysis (quantitative data), summary statistics will be calculated at each time point.

11.4.2.4. Height, Body Weight, and Vital Signs (Blood Pressure, Pulse Rate, and Body Temperature)

For blood pressure (systolic and diastolic), pulse rate, body temperature, and body weight, summary statistics of measured values and changes from baseline will be calculated at each time point.

11.4.2.5. Electrocardiogram

In the 12-lead ECG analysis on PR, QRS, RR, and QT intervals, QT corrected for heart rate using Bazett’s method (QTcB), QTcF, and heart rate, summary statistics of measured values and changes from baseline will be calculated at each time point. For QTcF, frequency tables will be prepared according to the following categories:

Absolute QTcF:

- QTcF >450 ms
- QTcF >480 ms
- QTcF >500 ms

Changes in QTcF from baseline:

- Increase in QTcF from baseline >30 ms
- Increase in QTcF from baseline >60 ms

11.4.3. Efficacy Analysis

The efficacy analyses will be performed on the efficacy analysis set, unless otherwise noted.

For the best response (CR, CRi, CRh, PR, MLFS, SD, and PD), frequency tables will be prepared. The point estimate and the 95% CI will be calculated for the CRc rate, response rate, and transplantation rate (as a subsequent AML treatment).

For the duration of CRc, summary statistics will be calculated using the Kaplan-Meier method.

11.4.4. Pharmacokinetic Analysis

Pharmacokinetics will be analyzed for each subtrial in the pharmacokinetic analysis set.

Summary statistics of plasma concentrations of DS-3032a will be calculated by dose at each time point, and a plasma concentration-time profile will be prepared.

For the pharmacokinetic parameters that are calculated by the non-compartmental analysis, summary statistics will be calculated by dose. The relationship between dose and each pharmacokinetic parameter will also be assessed.

11.4.5. Pharmacodynamic Analysis

For PDy values and PDy parameters, summary statistics will be calculated by treatment group. The time profile of PDy values will be prepared.

11.4.6. Other Analyses

Analyses using modeling and simulation, including population pharmacokinetic analysis and pharmacokinetic/pharmacodynamic analysis, will be performed using plasma DS-3032a concentration data, where appropriate. If the analyses are performed, the results will be separately reported.

11.5. Changes to the Analysis Plan

When it is considered necessary to change the analysis plan, the sponsor will discuss the appropriateness of the change and potential influences on evaluations in the study, and determine whether the change is feasible or not. The sponsor will clearly document and retain the content of the discussion about the change in the analysis plan, whether the change was made or not, and the reason for the change if it is made. The details of all changes in the analysis plan that have been made will be documented with the reasons in the clinical study report.

